## **6.6 Prohibited Medications**

Subjects are prohibited from receiving the following therapies during the Screening and Treatment Phase (including retreatment for post-complete response relapse) of this trial:

- Anti-cancer systemic chemotherapy or biological therapy
- Immunotherapy not specified in this protocol
- Chemotherapy not specified in this protocol
- Investigational agents other than Pembrolizumab
- Radiation therapy

- Note: Radiation therapy to a symptomatic solitary lesion or the brain may be allowed after consultation with the study PI and Merck.
- Live vaccines within 30 days prior to the first dose of trial treatment and while participating in the trial. Examples of live vaccines include, but are not limited to, the following: measles, mumps, rubella, chicken pox, yellow fever, rabies, BCG, and typhoid (oral) vaccine. Seasonal influenza vaccines for injection are generally killed virus vaccines and are allowed; however, intranasal influenza vaccines (e.g., Flu-Mist®) are live attenuated vaccines and are not allowed.
- Glucocorticoids for any purpose other than to modulate symptoms from an event of clinical interest of suspected immunologic etiology. The use of physiologic doses of corticosteroids may be approved after consultation with the study PI and Merck.

Subjects who, in the assessment by the investigator, require the use of any of the aforementioned treatments for clinical management should be removed from the trial. Subjects may receive other medications that the investigator deems to be medically necessary.

The Exclusion Criteria describes other medications, which are prohibited in this trial.

There are no prohibited therapies during the Post-Treatment Follow-up Phase.

## **7 Reporting and Documentation of Results**

### **7.1 Evaluation of Efficacy: Antitumor Effect – Solid Tumors**

Response and progression in this study will be evaluated using the new international criteria proposed by the revised Response Evaluation Criteria in Solid Tumors (RECIST) guideline (version 1.1). Changes in the largest diameter (unidimensional measurement) of the tumor lesions and the shortest diameter in the case of malignant lymph nodes are used in the RECIST v1.1 criteria.

#### **7.1.1 Definitions**

##### **Evaluable for toxicity**

All participants will be evaluable for toxicity from the time of their first treatment with pembrolizumab, vorinostat, and tamoxifen.

##### **Evaluable for objective response**

Only those participants who have measurable disease present at baseline, have received at least one cycle of therapy, and have had their disease re-evaluated will be considered evaluable for response. These participants will have their response classified according to the definitions stated below. (Note: Participations who exhibit objective disease progression prior to the end of Cycle 1 will also be considered evaluable.)

## **Evaluable Non-Target Disease Response**

Participants who have lesions present at baseline that are evaluable but do not meet the definitions of measurable disease, have received at least one cycle of therapy, and have had their disease re-evaluated will be considered evaluable for non-target disease. The response assessment is based on the presence, absence, or unequivocal progression of the lesions.

### **7.1.2 Disease Parameters**

#### **Measurable disease**

Measurable disease is defined as lesions (or tumors) that can be accurately measured in at least one dimension (longest diameter to be recorded) with a minimum size of 10mm by CT scan (irrespective of scanner type) and MRI (no less than double the slice thickness and a minimum of 10mm), 10mm caliper measurement by clinical exam (when superficial), and/or 20mm by chest X-ray (if clearly defined and surrounded by aerated lung).

All tumor measurements will be recorded in millimeters or decimal fractions of centimeters. Previously irradiated lesions are considered non-measurable except in cases of documented progression of the lesion since the completion of radiation therapy.

#### **Malignant lymph nodes**

To be considered pathologically enlarged and measurable, a lymph node must be  $\geq 15$  mm ( $\geq 1.5$  cm) in short axis when assessed by CT scan (CT scan slice thickness recommended to be no greater than 5 mm [0.5 cm]). At baseline and in follow-up, only the short axis will be measured and followed.

#### **Non-measurable disease (Tumor Markers)**

All other lesions (or sites of disease), including small lesions (longest diameter  $< 10$  mm [ $< 1$  cm] or pathological lymph nodes with  $\geq 10$  to  $< 15$  mm [ $\geq 1$  to  $< 1.5$  cm] short axis), are considered non-measurable disease. Bone lesions, leptomeningeal disease, ascites, pleural/pericardial effusions, lymphangitis cutis/pulmonitis, inflammatory breast disease, and abdominal masses (not followed by CT or MRI), are considered as non-measurable.

Note: Cystic lesions that meet the criteria for radiographically defined simple cysts should not be considered as malignant lesions (neither measurable nor non-measurable) since they are, by definition, simple cysts.

'Cystic lesions' thought to represent cystic metastases can be considered as measurable lesions if they meet the definition of measurability described above. However, if non-cystic lesions are present in the same patient, these are preferred for selection as target lesions.

#### **Target lesions**

All measurable lesions up to a maximum of 2 lesions per organ and 5 lesions in total, representative of all involved organs, should be identified as target lesions and recorded and measured at baseline. Target lesions should be selected on the basis of their size (lesions with the longest diameter), be representative of all involved organs, but in addition, should be those that lend themselves to reproducible repeated measurements. It may be the case that, on occasion, the largest lesion does not lend itself to reproducible measurement in which circumstance the next largest lesion which can be measured reproducibly should be selected. A sum of the diameters (longest for non-nodal lesions, short axis for nodal lesions) for all target lesions will be calculated and reported as the baseline sum diameters. If lymph nodes are to be included in the sum, then only the short axis is added into the sum. The baseline sum diameters

will be used as reference to further characterize any objective tumor regression in the measurable dimension of the disease.

### **Non-target lesions**

All other lesions (or sites of disease) including any measurable lesions over and above the 5 target lesions should be identified as non-target lesions and should also be recorded at baseline. It is possible to record multiple non-target lesions involving the same organ as a single item on the case record form (e.g. “multiple enlarged pelvic lymph nodes” or “multiple liver metastases”). Bone lesions may be measurable if  $\geq 1$  cm on MRI. Measurements of these lesions are not required, but the presence or absence of each will be noted throughout follow-up.

### **Non-measurable disease (Tumor Markers)**

Non-measurable disease is all other lesions (or sites of disease), including small lesions (longest diameter  $< 20$  mm with conventional techniques or  $< 10$  mm using spiral CT scan). Leptomeningeal disease, ascites, pleural or pericardial effusion, inflammatory breast disease, lymphangitic involvement of skin or lung, abdominal masses/abdominal organomegaly identified by physical exam that is not measurable by reproducible imaging techniques are all non-measurable (e.g., PSA, CA-125, CA19-9, CEA).

### **7.1.3 Methods for Evaluation of Measurable Disease**

All measurements will be taken and recorded in metric notation using a ruler or calipers. All baseline evaluations will be performed as closely as possible to the beginning of treatment and never more than 28 days before the beginning of the treatment.

The same method of assessment and the same technique will be used to characterize each identified and reported lesion at baseline and during follow-up. Imaging-based evaluation is preferred to evaluation by clinical examination when both methods have been used to assess the antitumor effect of a treatment.

**Clinical lesions:** Clinical lesions will only be considered measurable when they are superficial (e.g., skin nodules and palpable lymph nodes) and  $\geq 10$  mm ( $\geq 1$  cm) diameter as assessed using calipers (e.g., skin nodules). In the case of skin lesions, documentation by color photography, including a ruler to estimate the size of the lesion, is recommended.

**Chest x-ray:** Lesions on chest x-ray are acceptable as measurable lesions when they are clearly defined and surrounded by aerated lung. However, CT is preferable.

**Conventional CT and MRI:** This guideline has defined measurability of lesions on CT scan based on the assumption that CT slice thickness is 5 mm (0.5 cm) or less. If CT scans have slice thickness greater than 5 mm (0.5 cm), the minimum size for a measurable lesion should be twice the slice thickness. MRI is also acceptable in certain situations (e.g., for body scans).

Use of MRI remains a complex issue. MRI has excellent contrast, spatial, and temporal resolution; however, there are many image acquisition variables involved in MRI, which greatly impact image quality, lesion conspicuity, and measurement. Furthermore, the availability of MRI is variable globally. As with CT, if an MRI is performed, the technical specifications of the scanning sequences used should be optimized for the evaluation of the type and site of disease. Furthermore, as with CT, the modality used at follow-up should be the same as was used at baseline, and the lesions should be measured/assessed on the same pulse sequence. It is beyond the scope of the RECIST guidelines to prescribe specific MRI pulse sequence parameters for all scanners, body parts, and diseases. Ideally, the same type of scanner should

be used, and the image acquisition protocol should be followed as closely as possible to prior scans. Body scans should be performed with breath-hold scanning techniques, if possible.

#### **7.1.4 Response Criteria**

##### **Evaluation of Target Lesions**

###### Complete Response (CR)

Disappearance of all target lesions, determined by two separate observations conducted not less than 4 weeks apart. Any pathological lymph nodes (whether target or non-target) must have reduction in short axis to <10 mm (the sum may not be "0" if there are target nodes). There can be no appearance of new lesions.

###### Partial Response (PR)

At least a 30% decrease in the sum of the longest diameter (LD) of target lesions, taking as reference the baseline sum LD. There can be no appearance of new lesions.

###### Progressive Disease (PD)

At least a 20% increase in the sum of the diameters of target lesions, taking as reference the smallest sum on study (this includes the baseline sum if that is the smallest on study). In addition to the relative increase of 20%, the sum must also demonstrate an absolute increase of at least 5 mm (0.5 cm). (Note: the appearance of one or more new lesions is also considered progressions).

###### Stable Disease (SD)

Neither sufficient shrinkage to qualify for PR nor sufficient increase to qualify for PD, taking as reference the smallest sum LD since the treatment started.

##### **Evaluation of Non-Target Lesions**

###### Complete Response (CR)

Disappearance of all non-target lesions and normalization of tumor marker level. All lymph nodes must be non-pathological in size (< 10 mm short axis).

Note: If tumor markers are initially above the upper normal limit, they must normalize for a patient to be considered in complete clinical response.

###### Incomplete Response/Stable Disease (SD)

Persistence of one or more non-target lesion(s) and/or maintenance of tumor marker level above the normal limits.

###### Progressive Disease (PD)

Appearance of one or more new lesions and/or unequivocal progression of existing non-target lesions.

##### **Evaluation of Best Overall Response**

The best overall response is the best response recorded from the start of the treatment until disease progression/recurrence (taking as reference for progressive disease the smallest measurements recorded since the treatment started). The participant's best response assignment will depend on the achievement of both measurement and confirmation criteria.

**Table 7.1 Response Criteria for Participants with Measurable Disease (i.e., Target Disease)**

Target Lesions	Non-Target Lesions	New Lesions	Overall Response	Best Overall Response when Confirmation is Required*
CR	CR	No	CR	≥4 wks. Confirmation**
CR	Non-CR/Non-PD	No	PR	≥4 wks. Confirmation**
CR	Not evaluated	No	PR	
PR	Non-CR/Non-PD/not evaluated	No	PR	
SD	Non-CR/Non-PD/not evaluated	No	SD	Documented at least once ≥4 wks. from baseline**
PD	Any	Yes or No	PD	no prior SD, PR or CR
Any	PD***	Yes or No	PD	
Any	Any	Yes	PD	

\* See RECIST 1.1 manuscript for further details on what is evidence of a new lesion.

\*\* Only for non-randomized trials with response as primary endpoint.

\*\*\* In exceptional circumstances, unequivocal progression in non-target lesions may be accepted as disease progression.

Note: Participants with a global deterioration of health status requiring discontinuation of treatment without objective evidence of disease progression at that time should be reported as “*symptomatic deterioration*.” Every effort should be made to document the objective progression even after discontinuation of treatment.

**Table 7.2 Response Criteria for Participants with Non-Measurable Disease (i.e., Non-Target Disease)**

Non-Target Lesions	New Lesions	Overall Response
CR	No	CR
Non-CR/non-PD	No	Non-CR/non-PD*
Not all evaluated	No	not evaluated
Unequivocal PD	Yes or No	PD
Any	Yes	PD
* ‘Non-CR/non-PD’ is preferred over ‘stable disease’ for non-target disease since SD is increasingly used as an endpoint for assessment of efficacy in some trials so to assign this category when no lesions can be measured is not advised		

**Duration of Response**

Duration of overall response

The duration of overall response is measured from the time measurement criteria are met for CR or PR (whichever is first recorded) until the first date that recurrent or progressive disease is objectively documented (taking as reference for progressive disease the smallest measurements recorded since the treatment started).

The duration of overall CR is measured from the time measurement criteria are first met for CR until the first date that recurrent disease is objectively documented.

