### 2.2 Primary Objective and Endpoints

Primary Objective	Endpoint(s)	Time Frame
To define the role of epigenetic immune priming in a biomarker enriched ER+ breast cancer population on the basis of overall response rate	ORR: CR+PR+SD	From time of initial response to time of progression or death, whichever occurs first, assessed up to 24 weeks

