### 2.3 Secondary Objective(s) and Endpoint(s)

Secondary Objective	Endpoint(s)	Time Frame
1. To assess duration of response (DOR) 24-week landmark progression-free survival (PFS:24)	DOR (CR+PR)	From initiation of study treatment to time of progression or death, whichever occurs first, assessed up to 24 weeks
2. Median PFS and overall survival (OS)	
 
• Median PFS
 
• overall survival (OS)
 
	From initiation of study treatment to the time of death from any cause on study, assessed up to 48 months
3. Tumor responses will also be calculated by Immune Related Response-Criteria (irRC)	Tumor responses (irRC)	Through study completion, assessed up to 24 months

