### Progression-Free Survival

Progression-free survival (PFS) is defined as the duration of time from start of treatment to time of progression or death, whichever occurs first.

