### 8.3.3 Secondary Analysis (or Analysis of Secondary Endpoints)

We will use median (DOR, OS, PFS, computed by the Kaplan-Meier estimator) and percentages (% irRC) to summarize secondary endpoints. The respective confidence intervals will be computed as well.

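### Section 7.1.4 does not end duration of response at death, Section 2.3 does, and Section 8.3.3 does not say which rule the Kaplan-Meier median follows

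*Combined protocol and SAP*

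**What the plan says.** Four places bear on when a response ends.

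- **Section 7.1.4, Duration of Response.** Overall response runs from the first time CR or PR criteria are met "until the first date that recurrent or progressive disease is objectively documented". Duration of CR runs to objectively documented recurrence. Neither sentence mentions death.
- **Section 2.3, endpoint table, DOR (CR+PR) row.** The time frame is "From initiation of study treatment to time of progression or death, whichever occurs first, assessed up to 24 weeks". Death ends DOR here. The row also starts the clock at treatment rather than at response, and stops it at 24 weeks.
- **Section 8.3.3.** The analysis is one sentence: "We will use median (DOR, OS, PFS, computed by the Kaplan-Meier estimator) and percentages (% irRC) to summarize secondary endpoints". Confidence intervals are added, but the section does not define the DOR event or the censoring.
- **Section 7.1.4, Progression-Free Survival.** PFS is the "duration of time from start of treatment to time of progression or death, whichever occurs first", so death counts.

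Section 2.2 also carries a time frame that reads like one for DOR, "From time of initial response to time of progression or death, whichever occurs first, assessed up to 24 weeks", but it is attached to the primary response-rate endpoint.

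**The concern.** A Kaplan-Meier analysis censors anyone who leaves observation without the defined event. If the event is documented progression only, a responder's death is not an event, and the analysis treats that response as if it could have continued. Death in metastatic disease is not independent of loss of response, so the censoring would be informative and would tend to lengthen the median.

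The plan leaves room for such deaths. Section 7.1.4 (note to Table 7.1) recognises symptomatic deterioration without objective progression. Section 5.4 withdraws patients with clear clinical but unconfirmed radiographic progression. Section 3.5 and the Study Calendar allow later restaging to be spaced to every 6 cycles, which is 18 weeks.

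The point needs its own instruction. An obvious repair of the start date in Section 2.3 is to defer to Section 7.1.4, which starts at response. Done without further change, that would remove the one DOR-labelled entry that counts death.

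**Working it through.** **Step 1. Is there a figure to reproduce?** No. The documents give no expected DOR, no expected share of deaths and no precision target for DOR. The check is a comparison of rules plus an illustration of size.

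**Step 2. The rules side by side**

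| Source | Start | End | Death ends it? |
|---|---|---|---|
| 2.3, DOR row | Start of treatment | Progression or death, up to 24 weeks | Yes |
| 7.1.4, overall response | First CR or PR | Documented recurrence or progression | Not named |
| 7.1.4, CR | First CR | Documented recurrence | Not named |
| 7.1.4, PFS | Start of treatment | Progression or death | Yes |
| 8.3.3, DOR | Not stated | Not stated | Not stated |

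For a responder who dies without documented progression, PFS ends with an event at death. DOR ends with an event under Section 2.3 and would be censored under Section 7.1.4.

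**Step 3. Large-sample size**

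Assume constant hazards hP (documented progression) and hD (death without it), and let f = hD/(hP + hD).

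- Median with death as an event: ln 2/(hP + hD).
- Kaplan-Meier median with death censored: ln 2/hP.
- Ratio: (hP + hD)/hP = 1/(1 − f).

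The value of f is an assumption. The 10.3-month median response duration of the earlier vorinostat and tamoxifen trial (Section 1.3.1.3) is used only as a scale.

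| f | 1/(1 − f) | Increase | 10.3 months becomes |
|---|---|---|---|
| 0 | 1.000 | 0% | 10.3 |
| 0.05 | 1.053 | 5% | 10.8 |
| 0.10 | 1.111 | 11% | 11.4 |
| 0.20 | 1.250 | 25% | 12.9 |
| 0.30 | 1.429 | 43% | 14.7 |

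Simulated Kaplan-Meier medians with 100,000 responders per case agree: 10.8, 11.4, 12.9 and 14.8 months for f = 0.05, 0.10, 0.20 and 0.30.

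**Step 4. The sample this trial would have**

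Borrowing the 19% objective response rate of the same earlier trial, a full Arm A gives 0.19 × 35 = 6.65, about 7 responders. Suppose all 7 have an event and one is a death. With death counted, the median is the 4th ordered time. With the death censored, taking the first time at which the curve is at or below 0.5:

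- Death ranked 5th, 6th or 7th: the median stays at the 4th time.
- Death ranked 1st: the curve at the 4th time is 5/6 × 4/5 × 3/4 = 0.500, so it stays there under this convention.
- Death ranked 2nd: 6/7 × 4/5 × 3/4 = 0.514. Ranked 3rd: 6/7 × 5/6 × 3/4 = 0.536. Ranked 4th: 6/7 × 5/6 × 4/5 = 0.571. All exceed 0.5, so the median moves to the 5th time.

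With exponential times of rate λ, the expected 4th time is (1/7 + 1/6 + 1/5 + 1/4)/λ = 0.760/λ. The expected 5th time adds 1/3, giving 1.093/λ, and 1.093/0.760 = 1.44. So one death in seven leaves the median unchanged in four positions and moves it by roughly 44%, on expected times, in three. The large-sample formula at f = 1/7 would give 7/6 = 1.17. It does not predict the effect of a single death here.

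**The case against.** The strongest reply is that no section says deaths are censored. The row labelled as the DOR endpoint counts death, and an analyst could properly follow it. This stands. A reader might infer that the plan censors responders who die and that its DOR is therefore inflated. The documents do not support that. They support an unresolved conflict, with inflation only if Section 7.1.4 is the rule applied.

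The plan also limits how often the case arises. The note to Table 7.1 asks that progression be documented even after treatment stops. Section 3.6 follows patients who stop for other reasons until progression, new treatment, withdrawal or loss to follow-up. Both would lower f, though neither makes it zero.

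It is also fair to say that this should be settled together with the DOR start date and 24-week cap, since all three lie between Sections 2.3 and 7.1.4. That is an argument for one amendment, not for leaving the end event unsettled.

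Two further inferences fail. One is that the rule favours one treatment: the same definition applies to both arms, and no between-arm test of DOR is planned. The other is that toxic deaths make it worse: the pilot summaries report grade 3–4 toxicities and mention no toxic death.

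**Conclusion.** The point holds as a conflict between two stated rules, left open by the analysis section. Following Section 7.1.4 as written would give the worse result: informative censoring, a median DOR that tends to be too long, and a death treated differently in DOR and PFS.

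The size cannot be taken from the documents. The increase of 5% to 25% for f between 0.05 and 0.2 rests on an assumed f, constant hazards and a large sample. The count of about 7 responders is borrowed from a different regimen in patients not selected by this biomarker. At that count the effect of one death ranges from nil to more than the formula suggests.

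The consequence is limited. DOR is a secondary endpoint summarised descriptively, deaths still count in PFS and OS, and the primary response rate, the Simon boundaries and the power do not use DOR. The definition should be corrected, but the trial's main conclusion does not turn on it.

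**What to change.** - In Section 7.1.4, end both duration of overall response and duration of CR at the first of objectively documented progression or recurrence, or death from any cause.
- State that responders with neither event are censored at their last adequate disease assessment.
- Use this one definition in the DOR row of Section 2.3 and in Section 8.3.3, and settle the start date and the 24-week cap in the same amendment.

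The cost is a short amendment. Survival is already collected by telephone under Sections 3.6 and 6.3.3, so no new data collection is needed. The reported DOR may be slightly shorter than it would be under Section 7.1.4 as written.
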